## **8.10 Early Discontinuation of Study Treatment or Early Termination from the Study**

Subjects may prematurely discontinue study treatment for any of the following reasons:

1. Consent withdrawn for further study treatment (specify the reason).
2. Significant and unacceptable adverse event – specify the adverse event leading to discontinuation of study drug
3. Investigator decision (specify the reason), must be approved by the Medical Monitor
4. Non-compliance by subject with protocol requirements, must be approved by the Medical Monitor
5. Lost to follow-up (record the date of last contact)
6. Death (specify the following information)
  - a. Date of death
  - b. Death due to primary disease? Yes or no
  - c. Death due to study drug? Yes or no
  - d. Death due to adverse event? Yes or no
7. Lack of efficacy
8. Study terminated by the Sponsor
9. Other reason (specify the reason) should be approved by the Medical Monitor

The reason for discontinuation of study treatment will be documented for each subject. Subjects who discontinue study drug prematurely will not be replaced. At the time of discontinuation, please fill out the End of Study case report forms (eCRFs) and subject disposition eCRF pages.

Every effort will be made for the patient to complete all study related procedures at Day 15, Day 22, Day 29, Day 45, and Day 60. Every effort will be made to determine patient status (alive or dead) at Day 15, Day 22, Day 29, and Day 60. This determination can be made via telephone contact or public search records.

OF NOTE: For subjects who are terminated from the study prematurely, every effort should be made to have the subject complete all Early Termination Assessments (same as day 22 assessments). The reason for early termination from the study will be documented for each subject. Subjects who are early terminations will not be replaced. At the time of early termination, please fill out the Early Termination and End of Study case report forms.

Every effort should be made to determine patient status (alive or dead) at Day 60. This determination can be made via telephone contact or public search records.

### **8.11 Adverse Events**

An adverse event (AE) is any unfavorable or unintended change in body structure (signs) or body function (symptoms), abnormal laboratory result that is associated with symptoms or requires treatment or worsening of a pre-existing condition. This includes all such events regardless of the presumed relationship between the event and the study medication(s).

Any AE that occurs after the informed consent is signed but prior to dosing on Day 1 will be captured as part of the medical history and will be documented on the appropriate eCRF. This would include AEs resulting from concurrent illnesses, reactions to concomitant medications or progressive disease states.

Each subject will be assessed for the development of any adverse events. Adverse events should be assessed daily during the time in the hospital and at each visit to the clinic after discharge. This information should be obtained in the form of non-leading questions (e.g., "How are you feeling?") and from signs and symptoms detected during each examination, observations of the study personnel or spontaneous reports from the subjects.

Any AEs such as complaints, signs, or symptoms that occur during the course of the study or designated follow-up periods will be recorded on the subject's case report form (eCRF). This would include AEs resulting from concurrent illnesses, reactions to concomitant medications, or progressive disease states.

Whenever possible, the AE will be described on the case report form using standard medical terminology consistent with Common Terminology Criteria for Adverse Events (CTCAE) version 5 in order to avoid the use of vague, ambiguous or colloquial expressions. The investigator will evaluate all adverse events as to their intensity, relation to test medication, outcome and action taken.

Each AE will be evaluated for duration, intensity, and relationship to (or association with) the study treatment (or other causes). Additionally, the actions taken (e.g., reduction of dosage, discontinuation of study medication, administration of treatment, etc.) and the resulting outcome of the AE will be indicated on the case report form.

Any subject who is withdrawn from the study drug due to an adverse event will be followed until the outcome of the event is determined, and the investigator will prepare a written

summary of the event and document the available follow-up information on the case report form.

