### **8.9 Subject Stopping Rules**

If, in the opinion of the investigator, the participation in the study is or is becoming detrimental to the well-being of a particular subject, this issue should be discussed with the Medical Monitor for this study and dosing may be discontinued.

In subjects that experience an adverse event of Grade 4 or greater severity according to the Common Terminology Criteria for Adverse Events (CTCAE) version 5 ([https://evs.nci.nih.gov/ftp1/CTCAE/CTCAE\\_5.0\\_2010-06-14\\_QuickReference\\_5x7.pdf](https://evs.nci.nih.gov/ftp1/CTCAE/CTCAE_5.0_2010-06-14_QuickReference_5x7.pdf)) that is deemed to be possible, probably or definitely related to study drug dosing with study drug will be discontinued. Prior to discontinuation of study drug, the grading of the event and causal relationship should be discussed with the Medical Monitor for the study.

Subjects will be discontinued from dosing if AST or ALT levels are  $>5$  times the upper limit of normal, or if AST or ALT levels are  $>3$  times the upper limit of normal along with a total bilirubin elevation of  $>2$  times the upper limit of normal.

Subjects will be discontinued from dosing if Grade 3 diarrhea is observed.

Subjects will be discontinued from dosing if Grade 3 neutropenia is observed.

NOTE: These subject stopping rules are related to the discontinuation of study drug, not discontinuation from the study. Subjects should be followed for efficacy and safety even if study drug is stopped based on these stopping rules.

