6.14.1 Adverse Events

A treatment emergent adverse event (TEAE) is defined as:

- Any AE that has an onset on or after the first dose of study drug.
- Any pre-existing AE that has worsened in severity on or after the first dose of study drug.

A treatment-related AE is defined as an AE with causality collected as 'POSSIBLY RELATED', 'PROBABLY RELATED' or 'RELATED' in the CRF.

The intent is to collect all data, in a rare cases data might be incomplete for AE relationship and/or standard toxicity grade. This is not anticipated to cause any issues in the analysis and in these cases values will be imputed using worst-case scenario for analysis as follows:

- If an AE has missing relationship it is assumed to be 'RELATED' to the study drug for analysis purposes.
- If an AE has missing standard toxicity grade it is assumed to be 'GRADE 3 (SEVERE)' for analysis purposes. This is not worst case but more meaningful to impute as severe compared to life-threatening or death.

AEs will be summarized according to the MedDRA (version 24.0) system organ class and preferred term.

The following tables will be presented for AEs:

- Overall incidence and the number of events in the following categories:
 - TEAEs
 - Treatment-Related TEAEs
 - Serious TEAEs
 - Treatment-Related Serious TEAEs
 - TEAEs leading to treatment modification (drug interrupted / dose increased / dose reduced)

Controlled Quality Management Document		
	Sponsor:	Veru Inc.
	Protocol Number:	V3011902
STATISTICAL ANALYSIS PLAN. PHASE 2-3-4		

- TEAEs leading to treatment discontinuation (drug withdrawn)
- Fatal TEAEs
- For the above AE categories tables including incidence and number of events will be presented by system organ class and preferred term
- TEAEs by system organ class, preferred term and maximum toxicity grade (incidence, no event counts)
- TEAEs by system organ class, preferred term and strongest relationship grade (incidence, no event counts)
- Listing of Deaths (presented in the Table section of the appendices)
- Listing of Serious TEAEs (presented in the Table section of the appendices).

In counting the event number of AEs reported, a continuous event (i.e. reported more than once and which did not cease), will be counted only once; non-continuous AE reported several times by the same subject will be counted as multiple events.

All AEs will be listed.

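### A laboratory result that forces study drug to be stopped under protocol 8.9 need not be recorded as an adverse event under 8.11, and the SAP laboratory tables only partly make up for it

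*Protocol*

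**What the plan says.** Protocol 8.11 has a specific clause for laboratory findings, "abnormal laboratory result that is associated with symptoms or requires treatment", followed by a separate one for existing disease that worsens. It says nothing about a result that leads to a stop of study drug. The same section sets a follow-up duty, tied to an AE: "Any subject who is withdrawn from the study drug due to an adverse event will be followed until the outcome of the event is determined". The investigator must also write a summary of the event.

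Protocol 8.9 contains two stopping rules that rest on laboratory values. The first reads "Subjects will be discontinued from dosing if AST or ALT levels are" above 5 times the upper limit of normal (ULN), or above 3 times ULN together with total bilirubin above 2 times ULN. The second reads "Subjects will be discontinued from dosing if Grade 3 neutropenia is observed". A note adds: "Subjects should be followed for efficacy and safety even if study drug is stopped based on these stopping rules".

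Protocol 8.10 requires a documented reason for every stop of study drug. Where the reason is an AE, the site must "specify the adverse event leading to discontinuation of study drug".

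On reporting, SAP 6.14.1 builds its discontinuation and maximum-grade tables from treatment-emergent AEs. SAP 6.14.2 classes laboratory values as low, normal or high. Protocol 9.7 plans more for the liver: counts of ALT and AST at 3, 5 and 10 times ULN, a shift table in those categories, and a Hy's Law summary.

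**The concern.** The protocol treats these two laboratory findings as serious enough to end dosing automatically, yet its AE definition does not require either to be recorded as an AE. Readers of a study report usually look to the table of AEs leading to discontinuation for tolerability. Here that table could leave out stops made under the protocol's own rules.

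Recording could also vary between sites. A site that reads 8.11 literally enters no AE. A site that regards any protocol-driven stop as an AE enters one. The reported rate would then partly reflect how sites read the definition. The safety objective in protocol 4.3 covers tolerability and risk/benefit, so this bears on a stated aim of the trial.

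**Working it through.** The plan states no figure on this point, so there is none to reproduce. The check is a comparison of texts, with a little arithmetic on the visit schedule.

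**1. Can a subject meet 8.9 without meeting 8.11?** Take each route into the AE definition for a subject with a symptom-free, untreated result.
- *Symptoms:* neither 8.9 rule requires any.
- *Requires treatment:* 8.9 requires only that drug be stopped. In its list of actions taken, 8.11 names stopping study medication and giving treatment separately, so a stop does not count as treatment.
- *Worsening of a pre-existing condition:* this needs such a condition. Protocol 6.2.2 excludes hepatic impairment and, with an exception for treated and controlled hepatitis C, documented liver disease. This route will seldom apply to the liver rule.
- *Change in body structure or function:* 8.11 glosses these as signs and symptoms. If they covered every abnormal value, the laboratory clause would be redundant.

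So the result can satisfy 8.9 and none of the routes in 8.11. The Grade 3 diarrhea rule in 8.9 has no such gap, because diarrhea is itself a symptom.

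**2. How is the stop coded?** None of the nine reasons in 8.10 is that a stopping rule was met. Reason 2 needs an AE. Without one, the natural choices are investigator decision (reason 3) or other (reason 9).

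**3. Which outputs would show it?**

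| Output | Built from | Shows the stop or the value? |
|---|---|---|
| SAP Table 14.3.1.2.6, AEs leading to discontinuation | AE records | Not if no AE was entered |
| SAP Table 14.3.1.3.1, AEs by maximum grade | AE records | Not if no AE was entered |
| SAP 6.4 disposition, by arm | Reason for stopping | Yes, but probably under investigator decision or other |
| SAP Table 14.3.4.1 and Listings 16.2.8.1 and 16.2.8.2 | Laboratory data | Individual values, no rate by arm |
| SAP Tables 14.3.5.1.2 and 14.3.5.2.2, shifts | Laboratory data | Only as low or high |
| Protocol 9.7 ALT/AST multiples and Hy's Law | Laboratory data | Would show the liver values, but absent from SAP 6.14.2 and the SAP 11.1 table list |
| Neutrophil-grade summary | None planned | Absent from both documents |

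The three-level shift is coarse. Protocol 6.2.2 excludes ALT or AST only above 3 times ULN, so a subject may enter with a value above 1 and up to 3 times ULN. If that value later passes 5 times ULN, the table shows high at baseline and high afterwards, which is no shift at all. SAP section 9, which lists changes from the protocol analysis, does not mention dropping the 9.7 liver summaries.

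**4. What follow-up remains?** Protocol 8.5 to 8.7 schedule hematology and chemistry on Days 3, 9, 15, 22 and 29.
- Stopped on the Day 3 result: tests remain on Days 9, 15, 22 and 29.
- Stopped on the Day 15 result: tests remain on Days 22 and 29.
- Last possible dose is Day 21 and the last scheduled test is Day 29: 29 − 21 = 8 days. With the ±3-day window it is 26 − 21 = 5 to 32 − 21 = 11 days.
- Days 45 and 60 are telephone contacts without laboratory tests (8.8).

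Laboratory follow-up therefore exists, but it ends on a calendar day and not at a determined outcome.

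**The case against.** The strongest reply is that little is lost. The note in 8.9 keeps every subject stopped under these rules in safety follow-up, and 8.10 asks for every effort to complete study procedures through Day 60. Under reasons 3 and 9 the stop must be specified and goes to the Medical Monitor for approval, and SAP 6.4 tabulates withdrawal reasons by arm. Laboratory values are listed whether or not an AE exists. The monitoring committee sees unblinded safety data about every 4 weeks (9.7.1). All of this stands. A reader might infer that these subjects drop out of follow-up or that their results disappear, and the documents do not support either reading.

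A second reply is that the protocol's own language leans towards recording these results. The neutropenia rule is stated as a grade, grading is set out for AEs, and the fallback scale in 8.11.1 allows a Grade 1 event without symptoms. That makes the text ambiguous. It does not settle the question, because the scale applies once something is an AE and 8.11 decides what is one. The ambiguity is itself a reason to expect sites to differ.

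A third reply is that protocol 9.7 already covers the liver independently of AE reporting. It would, if the SAP carried it out, but the SAP does not include those summaries. For neutropenia there is no such plan in either document.

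**Conclusion.** The mismatch is real and worth correcting. Read literally, 8.11 lets a mandatory stop for AST/ALT or Grade 3 neutropenia go unrecorded as an AE. Two AE tables can then be incomplete, and the follow-to-outcome duty and written summary are not triggered. The remaining outputs give a reason category, individual values or a coarse shift. None gives a rate by arm at the stopping thresholds.

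This rests on two assumptions: that some subjects meet an 8.9 laboratory threshold without symptoms or treatment, and that some sites apply 8.11 as written. The documents give no frequency for either, so no size can be attached.

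Two stronger readings should be resisted. A reader might infer that all symptom-free laboratory abnormalities fall outside the definition, but those that require treatment are included. A reader might also infer a biased comparison between arms. The study is double-blind (7.1), so recording habits should not depend on arm. What is at risk is the completeness of the absolute rates and their consistency across sites.

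**What to change.** - **Protocol 8.11:** extend the laboratory clause so that an abnormal result is also an AE when it meets a discontinuation criterion in 8.9 or otherwise leads to interruption or discontinuation of study drug. Leave the 8.9 thresholds unchanged.
- **SAP 6.14.2 and 11.1:** add the ALT/AST counts and shift table by multiples of ULN and the Hy's Law summary from protocol 9.7, and add a neutrophil-grade shift table. Compute the multiples from each local laboratory's own limit, because 6.14.2 rescales values for the descriptive statistics. If the sponsor meant to drop the 9.7 summaries, SAP section 9 should say so.
- **Protocol 8.9, 8.11 and 8.11.1:** reconcile these sections on whether a subject stopped for a laboratory value falls under the follow-to-outcome duty, and for how long. That is a clinical decision for the sponsor, and no monitoring rule is proposed here.

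The cost is one added clause in the definition, a few more AE entries, two or three more tables, and a slightly higher reported rate of discontinuation for AEs. The SAP tables need no new data collection: Appendix A already includes ALT, AST, total bilirubin and the white cell differential. They would also cover subjects treated before an amended AE definition takes effect.

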### 8.11.1 Intensity of Adverse Events

The intensity of the AEs will be graded according to CTCAE version 5. For any adverse event that is not specifically covered in CTCAE version 5, the following criteria should be used:

Grade	Description
1	Mild; asymptomatic or mild symptoms; clinical or diagnostic observations only; intervention not indicated
2	Moderate; minimal, local or noninvasive intervention indicated; limiting age-appropriate instrumental activities of daily living
3	Severe or medically significant but not immediately life-threatening; hospitalization or prolongation of hospitalization indicated; disabling; limiting self-care activities of daily living
4	Life-threatening consequences: urgent intervention indicated.
5	Death related to AE

If the intensity (Grade) changes within a day, the maximum intensity (Grade) should be recorded. If the intensity (Grade) changes over a longer period of time, the changes should be recorded as separate events (having separate onset and stop dates for each grade).

### 8.11.2 Test Medication Causality

The relationship (or association) of each AE to the test medication will be assessed by the investigator according to the following definitions:

**Unrelated:** There is no chance that the study medication caused the AE; other conditions, including concurrent illnesses, progression or expression of the disease state, or a reaction to a concomitant medication best explain the event.

**Unlikely:** There is little chance that the study medication caused the AE; other conditions, including concurrent illnesses, progression or expression of the disease state, or a reaction to a concomitant medication best explain the event.

**Possible:** The association of the AE with the study medication is unknown; however, the AE is not clearly due to another condition.

**Probable:** A reasonable temporal association exists between the AE and treatment administration and, based on the investigator's clinical experience, the association of the AE with the study treatment seems likely.

Veru Inc  
Protocol V3011902 – FINAL Version 7.0

**Definite:** The association of the AE with the study medication has a direct relationship.

For the purpose of safety analyses, all AEs which are classified as "Possible," "Probable" or "Definite" will be considered treatment-related events.

### 8.11.3 Serious Adverse Events

A **serious adverse event (SAE)** is defined as any experience that suggests a significant clinical hazard, contraindication, side effect, or precaution. This includes any event which:

- Results in death.
- Is life-threatening.
- Requires inpatient hospitalization or causes prolongation of existing hospitalization
- Results in persistent or significant disability/incapacity.
- Results in congenital abnormality/birth defect.
- Requires intervention to prevent permanent impairment or damage

An SAE also may include other events, based on medical judgment, which jeopardize the subject and require medical or surgical intervention to prevent one of the outcomes listed above.

Any SAE, including death due to any cause, which occurs during the study or within 60 days following initiation of dosing on study medication, whether or not related to the study medication, must be reported immediately via telephone (within 24 hours) to Veru Inc. Drug Safety.

In addition, the investigator must immediately complete a Serious Adverse Event eCRF report form and electronically submit the form. The investigator will promptly notify the Institutional Review Board (IRB).

If additional information regarding a previously submitted SAE is obtained, a follow-up SAE eCRF report should be completed and submitted as indicated above. Supporting source documentation should be provided to [REDACTED] Drug Safety at the contact information below.

- [REDACTED]
- [REDACTED]

[REDACTED]

[REDACTED]

[REDACTED]

[REDACTED]

#### **8.11.4 Initial Reports**

SAEs will be collected from the time of first study drug administration through 60 days after first study drug administration. SAEs and events of clinical interest must be reported to the Sponsor (or designee) within 24 hours of the knowledge of the occurrence.

In the event an SAE is observed or reported, the SAE report will be completed as thoroughly as possible including all available details about the event and the signature of the Investigator. If the Investigator does not have all information about an SAE, the Investigator will not wait to receive additional information before notifying the Sponsor of the event and completing the form. The form will be updated when additional information is received.

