### 6.2 Selection Criteria

#### 6.2.1 Inclusion Criteria

Subjects accepted for this study must:

1. Provide informed consent from the subject or the subject's Legally Authorized Representative (LAR)
2. Aged  $\geq 18$  years
3. Severe Acute Respiratory Syndrome Coronavirus (SARS-CoV-2) infection confirmed by polymerase chain reaction (PCR) test
4. Patients with a WHO Ordinal Scale for Clinical Improvement score of 4 at high risk for ARDS, must have at least one of the known comorbidities for being at high risk, such as, Asthma (moderate to severe), Chronic Lung Disease, Diabetes, Hypertension, Severe Obesity (BMI  $\geq 40$ ), 65 years of age or older, primarily reside in a nursing home or long-term care facility, or immunocompromised and patients with a WHO Ordinal Scale for Clinical Improvement score of 5 or 6 regardless of presence of comorbidities.
5. WHO Ordinal Scale for Clinical Improvement score of 4 (Oxygen by mask or nasal prongs), 5 (Non-invasive ventilation or high-flow oxygen) or 6 (Intubation and mechanical ventilation)
6. Peripheral capillary oxygen saturation ( $\text{SpO}_2$ )  $\leq 94\%$  on room air at screening. If patient is on oxygen therapy at the time of presentation for screening and the  $\text{SpO}_2$  levels were  $\leq 94\%$  prior to introduction to oxygen therapy with proper documentation example EMT notes or ER/ED notes, then the patient is considered to have met this inclusion criterion. If patient is on oxygen therapy at the time of presentation for screening and the  $\text{SpO}_2$  levels prior to introduction to oxygen therapy are unknown, the patient may be considered to have met this inclusion criterion if oxygen therapy is removed and the  $\text{SpO}_2$  levels fall to  $\leq 94\%$ , then the patient is considered to have met this inclusion criterion. However, removal of the oxygen therapy should only be done if it is considered medically reasonable.
7. Subjects must agree to follow doctor's recommendation for oxygen supplementation.
8. Subjects must agree to use acceptable methods of contraception:
  - If female of childbearing potential or a male subject's partner could become pregnant, use acceptable methods of contraception from the time of the first administration of study medication until 6 months following administration of

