## **8.0 STUDY PROCEDURES**

### **8.1 Screening**

Potential subjects will be screened for this study in the 3 days prior to enrollment. The following activities will be conducted at screening:

1. Signed informed consent and HIPAA form (or legal documents as directed based on the region outside of the United States) will be obtained prior to any study-specific procedures and a copy of the signed consent form will be given to the subject.
2. Assess subject eligibility for inclusion into this study based on protocol inclusion/exclusion criteria.
3. Pregnancy test (women of childbearing potential only)
4. Medical history will be obtained, including diagnosis of COVID-19 infection (date of diagnosis), details and dates of treatments received, documentation of symptoms related to COVID-19 infection, and COVID-19 vaccination status.
5. WHO Ordinal Scale score assessment
6. The use of any medications will be recorded. This will include medications currently being taken and those taken since COVID-19 symptoms started. Over-the-counter (OTC) medications as well as medications taken on an as-needed basis (PRN) should be recorded.
7. Vital signs (temperature/pulse/supine, if possible, blood pressure)
8. SpO2 level (%)

9. Physical examination including height and weight
10. Electrocardiogram- 12 lead (single)
11. Clinical Laboratory Tests
  - Hematology ([Appendix A](#))
  - Serum chemistry ([Appendix A](#))
  - Urinalysis

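### Protocol 8.11 and 8.11.4 contradict 8.11.3 on when SAE reporting starts, so serious harm from a screening procedure could go unreported as an SAE

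*Protocol*

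**What the plan says.** Three places in the Protocol set the start of safety reporting.

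- Section 8.11.4: "SAEs will be collected from the time of first study drug administration through 60 days after first study drug administration".
- Section 8.11: an adverse event with onset after consent but "prior to dosing on Day 1 will be captured as part of the medical history". There is no exception for serious events or for events caused by a study procedure.
- Section 8.11.3: any SAE "which occurs during the study or within 60 days following initiation of dosing on study medication", whether or not related to study medication, goes to the sponsor's drug safety group by telephone within 24 hours. An SAE form and prompt IRB notification follow.

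The screening list in 8.1 contains no adverse event assessment, and the adverse event row of Appendix B is blank at Screening; its first mark is at Day 1.

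Inclusion criterion 6 places a procedure in this interval. Where a patient is already on oxygen and the saturation before oxygen is unknown, "the patient may be considered to have met this inclusion criterion if oxygen therapy is removed and the" saturation then falls to 94% or below. The protocol adds that "removal of the oxygen therapy should only be done if it is considered medically reasonable". On timing, section 8.1 states: "Potential subjects will be screened for this study in the 3 days prior to enrollment". Consent must precede any study-specific procedure.

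In the SAP, a TEAE needs onset or worsening on or after first dose (6.14.1), and the safety analysis set needs randomization and at least one dose (6.1.4).

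**The concern.** A site with a patient who deteriorates seriously between consent and first dose finds two instructions. One says telephone within 24 hours; the other says record it as medical history. The second is the more specific, because 8.11 names exactly that interval and 8.11.4 gives a dated window.

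The interval is not empty. Criterion 6 permits a step taken to establish eligibility, in a population defined by WHO scores 4 to 6, all of which involve oxygen or ventilatory support. The protocol's own caution about that step acknowledges that it carries risk. If harm from it is filed as history, the sponsor's drug safety group and the IRB may not hear of it promptly, the IDMC may not receive it among the SAEs it reviews under 9.7.1, and an effect of a trial procedure may appear in the report as pre-existing disease.

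**Working it through.** No statistical figure is at stake, so the check compares the passages.

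1. **Do the sections give the same start point?** 8.11.4: first dose. 8.11: before first dose, medical history. 8.11.3 has two limbs joined by *or*: in the course of the study, or within 60 days of starting dosing. The second limb matches the 8.11.4 window. The first must add something, and the pre-dose period is the obvious candidate.

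2. **Does the study include screening?** Section 5.2 counts duration from screening to about Day 60 and gives approximately 62 days. Up to 3 days of screening before Day 1, plus 60 − 1 = 59 days from Day 1 to Day 60, gives 3 + 59 = 62. Without screening the figure would be 59 elapsed days. The protocol's own total therefore includes the pre-dose period, which favours reading 8.11.3 as covering it. Against this, the Procedures row of the Protocol summary has subjects enrolled into the study once they have consented and met the selection criteria, so a site may regard a patient still in screening as not yet in it. 8.11.3 does not define the term.

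3. **Does oxygen removal under criterion 6 fall in the disputed interval?** Done for eligibility, it follows consent (8.1) and precedes enrollment (8.2) and the first dose (8.3). It does.

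4. **If a site follows 8.11 and 8.11.4, where would a serious event appear?**
   - *Never randomized:* outside the ITT and safety sets and every TEAE table. The SAP counts and lists screen failures (6.4, section 11) but plans no safety summary for them.
   - *Randomized, never dosed:* in the ITT set, so a death counts in the primary endpoint, but outside the safety set and TEAE tables.
   - *Later dosed:* in the safety set, but the event is not a TEAE unless it worsens after dosing. SAP 6.7 tabulates it as a previous or ongoing condition.

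5. **Could procedure-relatedness be recorded?** The causality scale in 8.11.2 grades only the relation to study medication. It has no category for a study procedure.

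If a site follows 8.11.3 and counts screening as part of the study, all three kinds of patient in step 4 are reported within 24 hours. The outcome depends on which section the site follows.

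**The case against.** A reader might infer that such harm would never be reported as an SAE. The documents do not support that. 8.11.3 requires expedited reporting regardless of relation to the drug, and step 2 shows that its wording plausibly reaches screening. The event is also recorded on an eCRF, though as history. The supportable claim is that reporting could fail under one of two conflicting instructions.

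A reader might also infer that oxygen removal is the only pre-dose procedure carrying risk. Section 8.3 lists a chest X-ray or CT scan and blood sampling ahead of the first dose, so oxygen removal is an example only. It is also a fallback: it applies only when prior saturation is unknown and removal is judged medically reasonable, and documentation such as ambulance or emergency department notes makes it unnecessary.

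Some capture exists elsewhere. Day 1 asks about ongoing adverse events. The WHO score is taken at Screening and again on Day 1, so an intubation in between shows in anyone who reaches Day 1. The IDMC's remit under 9.7.1 is unblinded safety data including SAEs, which is not limited to SAEs. These points stand and narrow the concern, but none replaces expedited reporting and none covers a death in screening before randomization.

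Finally, a rule limited to procedure-related SAEs and deaths would be narrower than 8.11.3, which ignores relation to study medication. That is correct, so the fix states it as a minimum.

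**Conclusion.** This is an internal inconsistency with a safety consequence. 8.11 and 8.11.4 place the start of SAE reporting at first dose; 8.11.3, on its more natural reading, places it earlier. A site following the more specific pair could leave a serious screening-procedure event unreported as an SAE, and the SAP's safety set and TEAE rules would not recover it in an undosed patient.

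No number of patients or events can be attached, because the documents do not say how many would need the oxygen test or how often harm would follow. The extent is a period: up to 3 days of screening, plus any time between randomization and first dose. The conclusion assumes that some sites would follow 8.11 and 8.11.4; it does not assume that all would. It does not affect the primary analysis, and it makes no judgement on criterion 6 as a clinical rule.

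**What to change.** Amend 8.11, 8.11.3 and 8.11.4 to one start point for SAE reporting, at signed consent.

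- At minimum, any death and any SAE related to a protocol procedure between consent and first dose, with oxygen removal under criterion 6 named explicitly, is reported within 24 hours on the SAE form. Screen failures are included. If the sponsor intends 8.11.3 to govern in full, all pre-dose SAEs are reported, and 8.11 and 8.11.4 should say so.
- Other pre-dose adverse events can stay in medical history.
- Add an adverse event mark at Screening in Appendix B and a matching item in 8.1.
- In the SAP, list these events separately from TEAEs, for all consented subjects (the Enrolled Set already defined in 6.1.1).

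The cost is a short amendment, an added listing and probably a few extra SAE reports. The TEAE definition and tables, the safety set and the efficacy analyses do not change.
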